In this 3 x 2 design, patient participants (N = 150) will be randomly assigned to receive treatment modules sequenced according to the following three module-ordering conditions: 1) Standard: In accordance with the standard, published UP manual; 2) Capitalization: organized to prioritize skills that capitalize on patient strengths; 3) Compensation: organized to prioritize skills that compensate for patient weakness. All participants will also be randomized to two treatment-duration conditions: 1) Brief: 7 sessions; or 2) Full: 13 sessions. Deception will not be used – patients will be fully informed about the possibility of being assigned to the Brief or Full treatment length condition. However, during the consent process, we have elected to limit the information provided about each ordering scheme. Instead, participants will be told that we may use their self-report questionnaire data to determine the order of their skills. This omission of information is justified for the following reasons: 1) knowing their condition may bias results and, given that the conditions are face valid, patients may be able to guess their assignment if they are provided detailed information about the possibilities, and; 2) although research provision of manualized interventions (like the UP) are typically delivered in a standard order, it is common in routine practice for therapists to make decisions about how to order treatment skills without providing patients with reasoning. Following the final assessment, patients will be provided with information about the three module-ordering conditions and the condition to which they had been assigned will be revealed.

Clinician participants will not be randomized - all clinicians will be asked to attend a training workshop in the Unified Protocol and participate in weekly consultation calls with [name] or [name]. They will provide care in each patient condition (standard, capitalization, compensation; brief, full). Clinicians will be asked to complete surveys and interviews about their impressions participating in this study/providing care based patient strengths/weaknesses.

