Following Assessment Visit 1, all participants will begin completing weekly treatment sessions in person, via phone, or via HIPAA-compliant video conferencing service (i.e., Zoom via the UK HealthCare portal); the order of treatment skills will be determined based on their assignment to module-ordering condition. Before the start of Treatment Session 5, clinician participants will alert study staff (i.e., research assistant) to request a randomization to a Treatment Length Condition: Brief (6 sessions) or Full (12 sessions). Treatment Length Randomization will occur at this stage to limit expectancy effects on therapists' and participants' behaviors, while also allowing therapists and participants to plan their final 2 sessions together with this randomization in mind. Participants randomized to the Brief treatment condition be reminded during Treatment Session 6 how they can use the skills learned in the previous sessions in the upcoming weeks to prevent relapse. In the event that participants are at an imminent risk of harm to themselves or others at this session, the therapist will work with the PI to develop a safety plan with the participant which may include referrals to other psychotherapy resources or hospitalization.

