We will use a treatment window during which the assigned number of sessions will be completed; specifically, patients randomized to the Brief condition will complete 7 sessions during an 10-week window and patients randomized to the Full condition will complete 13 sessions during a 20-week window. This will allow us to account for scheduling challenges (e.g., patient/therapist illness, vacation). The first session for all participants will be an "orientation to treatment" session in which presenting concerns will be reviewed and an overview of the treatment model will be provided. As noted previously, the skills delivered during the remaining sessions in this study will be drawn from the UP. Four of the five UP modules will be implemented 2 sessions: Understanding Emotions, Mindful Emotion Awareness, Cognitive Flexibility, and Increasing Interoceptive Tolerance. The 5th UP module, Countering Emotional Behaviors, is designed to be implemented in 4 sessions. All sessions will last for 60 minutes in duration. Thus, depending on treatment length and module order, each participant will receive 2 to 5 UP modules during this study. It is important to note that the therapeutic strategies involved in all modules are all common, evidence-based cognitive-behavioral strategies and are not, themselves, under study; instead, we are interested in whether personalized sequencing leads to faster improvements (not whether patients improve at all - we expect that most will improve). Every module involves reading from a published manual (the Unified Protocol for the Transdiagnostic Treatment of Emotional Disorders; Barlow et al., 2018) and completing homework assignments outside of the treatment session (this intervention has previously been reviewed by UK's non-medical IRB). These treatment sessions will be audio-recorded provided participants give their consent for this; this will allow study staff to rate sessions for fidelity to the protocol.

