Regardless of randomization, all participants will be scheduled for Assessment Visit 2 to occur between treatment sessions 5 and 6. Participants will complete an interview-based diagnostic assessment with a study assessor that will focus on the diagnoses assigned at Assessment Visit 1. This assessment may take place in person at UK psychiatry, over the phone, or via HIPAA-compliant Zoom. This assessment visit will be audio-recorded. Participants will also complete the same battery of self-report questionnaires at this visit as at Assessment Visit 1. All participants will also complete Assessment Visit 3, which will take place between weeks 13-16 (corresponding to the end of the treatment window for the Full length condition). This assessment visit will also be audio-recorded and may take place in person at UK Psychiatry, over the phone, or via HIPAA-compliant Zoom. Finally, Assessment Visit 4 will take place (in person at UK Psychiatry, over the phone, or via HIPAA-compliant Zoom) between 46 and 50 weeks after Assessment 1 and will include the same questionnaires.

Following the last treatment session (Treatment Session 13 for participants in the Full treatment condition; Treatment Session 7 for participants in the Brief treatment condition), participants will be asked to provide satisfaction ratings and written qualitative feedback on their experience with the treatment they received. Additionally, all participants will be asked to complete a weekly self-report battery assessing symptoms, skill proficiency, and skill knowledge for 20 weeks (again corresponding to the treatment window for the Full length condition); patients in the Brief condition will continue to complete these questionnaires after discontinuing treatment. These questionnaires will be emailed to participants and we will ask that they are completed within two days of receipt.

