**Pilot Test of Personalization Aims (ordering and discontinuation).** In addition to our primary aim of establishing the feasibility/acceptability of our personalization strategies and study design, we seek to determine whether a preliminary signal exists to support the notion that personalized sequencing and target-informed discontinuation can enhance treatment efficiency. First, to explore whether personalized sequencing leads to more efficient improvements in the core process addressed by the UP, we will use hierarchical linear mixed modeling (HLMM) to compare the average rate of change in clinical outcomes among the three UP sequencing conditions (UPS, UPP-CA, and UPP-CO). The primary outcome measure for aim is the distress aversion subscale from the MEAQ (MEAQ-DA), which has previously been used to demonstrate target engagement with the UP (see Preliminary Studies). Additionally, to examine whether core process engagement can serve as an early indicator of treatment response, prompting discontinuation, we will assess variability in MEAQ-DA levels at the second stage randomization (S5 assessment), along with the degree to which any patients randomized to discontinue demonstrate additional symptom improvement (using HAM-A ratings) in the absence of treatment such that they are responders by the W20 assessment. We will also explore whether patterns exist between S5 MEAQ-DA scores and responder status for those that discontinued after session 6.

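### HAM-A is not rated when Brief treatment stops, so HAM-A change up to W20 includes one or two treated sessions and cannot be labelled off-treatment change

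*Combined protocol and SAP*

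**What the plan says.** **The analysis.** Under Pilot Test of Personalization Aims in Statistical Design, the plan examines the degree to which any patients randomised to discontinue "demonstrate additional symptom improvement (using HAM-A ratings) in the absence of treatment such that they are responders by the W20 assessment". No starting HAM-A is named and no responder definition is given. A separate sentence relates S5 MEAQ-DA scores to "responder status for those that discontinued after session 6".

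**When HAM-A is rated.** The measure lists in Data Collection & Research Materials put HAM-A under the assessment visits. It is in neither the weekly pre-session list nor the weekly post-session list. The pre-session list does include OASIS and ODSIS.

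**When the visits fall.** Research Procedures states that "all participants will be scheduled for Assessment Visit 2 to occur between treatment sessions 5 and 6", whatever the arm. It then describes "Assessment Visit 3, which will take place between weeks 13-16", and a Visit 4 at 46 to 50 weeks. After the last session only satisfaction ratings and written feedback are added. Brief patients go on completing the weekly self-report battery to week 20.

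**How long Brief is.** The documents give two counts. Study Design has "Brief: 7 sessions; or 2) Full: 13 sessions", and Research Procedures agrees in one place: "patients randomized to the Brief condition will complete 7 sessions during an 10-week window". Elsewhere Research Procedures has "Brief (6 sessions) or Full (12 sessions", and Statistical Design also has patients stopping after Session 6.

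**The concern.** To show improvement without treatment, the change has to start from a rating made at or after the last session. No such HAM-A is scheduled before Visit 3. If the change is counted from Visit 2, the latest rating available, a Brief patient who crosses the response line because of Session 6 or 7 would be described as having improved after treatment ended.

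What is at stake is the wording of one exploratory result. The analysis is meant to indicate whether patients keep improving after stopping, and Power Analyses says the pilot's data will help decide whether further testing is warranted. A treated gain reported as an untreated one would overstate that signal.

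**Working it through.** **Step 1: is there an untreated HAM-A interval that ends by W20?**

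| Interval | Treated sessions inside it | Ends by W20? |
|---|---|---|
| Visit 1 to Visit 3 | All Brief sessions | Yes |
| Visit 2 to Visit 3 | Session 6, or Sessions 6 and 7 | Yes |
| Visit 3 to Visit 4 | None | No (weeks 46-50) |

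Visit 2 follows Session 5, so the number of treated sessions still to come is the Brief length minus 5: 6 - 5 = 1, or 7 - 5 = 2. As a share of sessions this is 1/6 = 17% or 2/7 = 29%. No scheduled interval is both untreated and complete by W20. This result needs no assumption about effect size.

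**Step 2: how long is the untreated time before the endpoint?** Assume weeks count from Session 1 and Brief ends no later than week 10.
- With Visit 3 at weeks 13-16: shortest 13 - 10 = 3 weeks; longest 16 - 6 = 10 (6 sessions) or 16 - 7 = 9 (7 sessions).
- With the rating at week 20: shortest 20 - 10 = 10; longest 20 - 6 = 14 or 20 - 7 = 13.

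The documents do not settle which applies. Visit 3 is said to match the end of the Full window, but "patients randomized to the Full condition will complete 13 sessions during a 20-week window", and Statistical Design refers to W20.

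**Step 3: how many responders could be misattributed?** The plan gives no figure to reproduce, so every input here is an assumption. Response is a 50% HAM-A fall from baseline. The total fall over Brief is normal with mean 40% and SD 25 percentage points. Nothing changes after the last session. Each session gives a fraction d of the gain of the one before it.

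Share of the gain falling after Visit 2, for n sessions: s = (d^5 + ... + d^(n-1)) / (d^0 + ... + d^(n-1)).

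A patient is misattributed if the total fall T reaches 0.5 but the fall by Visit 2, (1 - s)T, does not. That means 0.5 <= T < 0.5/(1 - s). The proportion is Phi((0.5/(1 - s) - 0.4)/0.25) - Phi((0.5 - 0.4)/0.25).

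Example with n = 6 and d = 1: s = 1/6, so 0.5/(1 - s) = 0.60, and Phi(0.80) - Phi(0.40) = 0.788 - 0.655 = 0.133.

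| Brief length | d | Share s | Misattributed | Of 25 patients |
|---|---|---|---|---|
| 6 | 1.0 | 16.7% | 13.3% | 3.3 |
| 6 | 0.8 | 8.9% | 6.9% | 1.7 |
| 6 | 0.6 | 3.3% | 2.4% | 0.6 |
| 7 | 1.0 | 28.6% | 23.0% | 5.7 |
| 7 | 0.8 | 14.9% | 11.8% | 3.0 |
| 7 | 0.6 | 5.1% | 3.9% | 1.0 |

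Varying the mean fall over 30-50% and the SD over 20-30 points, across all three values of d, gives 2-19% for 6 sessions and 3-34% for 7.

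The 25 is half of the 50 enrolled subjects in the continuation review, with equal allocation assumed. It is a ceiling. Some of the 50 may have been ineligible after Visit 1 or have left before the length randomisation at Session 5, and it is not stated whether the 50 includes clinicians.

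**The case against.** **The analysis is descriptive and names no starting rating.** Misattribution happens only if the analyst credits all Visit 2 to Visit 3 change to untreated time. That is true, so the consequence is an inference. But no scheduled HAM-A start would make the plan's description correct.

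**The remaining sessions belong to Brief.** Someone who responds because of Session 6 or 7 is a genuine Brief responder. This stands, and it limits the point: the responder classification is not wrong, only its description as untreated improvement. A reader might go further and infer that the design is tilted towards early stopping. The documents do not support that, because this analysis makes no Brief-versus-Full comparison.

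**The MEAQ-DA analysis.** A reader might also infer that relating S5 MEAQ-DA to responder status is compromised. It is not. That analysis asks whether the S5 score goes with the outcome of a Brief course, and it makes no off-treatment claim, so the remaining sessions belong in it.

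**Equal gain per session is unlikely.** Potential Risks & Benefits says much of the improvement comes in the first five sessions, and part of Session 6 in Brief goes to relapse-prevention reminders. This also stands. It favours the d = 0.6 rows, about one patient or fewer of 25, over the upper rows.

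**Conclusion.** The point holds as a matter of schedule: HAM-A change that spans the end of Brief and finishes by W20 contains one or two treated sessions and should not be reported as occurring without treatment.

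Its size is unknown. Under the assumed inputs it is about 2-13% of Brief patients with 6 sessions and 4-23% with 7, or roughly 1-3 and 1-6 of at most about 25 patients, with the low end more consistent with early gains. The percentages illustrate and do not estimate, since the plan defines no responder and gives no effect size. It would be wrong to quote the upper figures as an expected error rate: they need equal gains in every session, and the highest also need the 7-session count, whereas Statistical Design uses 6.

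The importance is minor. Feasibility and acceptability are the primary aim, and no test or stopping decision rests on this analysis.

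**What to change.** Amend the discontinuation paragraph in Statistical Design as follows.

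1. Start the off-treatment period at each Brief patient's last attended session. This works under either session count.
2. Describe off-treatment change from the first weekly OASIS and ODSIS after that session to week 20. The weekly forms are pre-session, so the form for the last session itself comes before it and is the wrong anchor.
3. Report HAM-A responder status at Visit 3 as the outcome of the whole Brief course, with weeks since the last session and the Visit 3 timing actually used.
4. Do not call the Visit 2 to Visit 3 HAM-A change untreated.

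The cost is a change of wording. No visit, new data or change to randomisation is needed, and it can be applied to patients already treated, because Brief patients complete the weekly forms to week 20. The downside is that off-treatment change then rests on self-report and is described as change, not as conversion to HAM-A response. Keeping that question on HAM-A would need one extra rating, for example by phone, after the last Brief session.

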This protocol reflects similar procedures to previously approved protocol #53545; however, instead of being conducted in the PI's lab space, this study will take place at in UK Psychiatry's Adult Outpatient clinic. The primary purpose of this study is to explore whether the efficiency of treatment for anxiety and depressive disorders can be increased using two discrete strategies: personalized skill ordering and 2) treatment discontinuation based on proximal indicators of improvements. The present study will specifically use treatment components drawn from an evidence-based psychological intervention, the Unified Protocol for the Transdiagnostic Treatment of Emotional Disorders (UP; Barlow et al 2011; 2018). This intervention has strong empirical support for patients presenting with anxiety, depressive, and related disorders (see: Barlow et al., 2017) and contains therapeutic skills that are common in psychological interventions (e.g., psychoeducation, mindfulness training, cognitive restructuring, counteracting emotional avoidance, increasing interoceptive tolerance). Skill modules in the UP are typically delivered in a standard order. Recent research conducted by the PI has shown that each UP module, when presented in isolation, leads to change in its associated skill (e.g., the mindfulness module leads to increased mindfulness), as well as improved symptoms ([name] et al., 2017). Given this evidence that each skill is self-contained, the PI recently conducted a pilot study personalizing the sequencing of UP modules ([name] et al., 2019). Specifically, a small sample (n=12) was randomly assigned to receive UP skills in an order that prioritized relative strengths vs. relative weaknesses. Results suggest that it is feasible to order modules in this manner, that patients were satisfied with their personalized order, and that, by the final session, patients in both conditions demonstrated similar levels of symptom improvement (comparable to effects for the standard presentation of the UP). There was also preliminary evidence to suggest that capitalizing on patient strengths is associated with steeper trajectories of change (i.e., faster symptom improvement) compared to compensating for deficits.

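### The discontinuation analyses look only at patients who stopped, so they can show prognosis after brief treatment but not whether MEAQ-DA should guide stopping

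*Combined protocol and SAP*

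**What the plan says.** The Background section of the Research Description names two strategies for making treatment more efficient. One of them is "treatment discontinuation based on proximal indicators of improvements". The Statistical Design section turns this into a preliminary-signal aim, secondary to feasibility and acceptability: "to examine whether core process engagement can serve as an early indicator of treatment response, prompting discontinuation".

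Three pieces of work serve that aim:

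1. The spread of MEAQ-DA at the second-stage randomisation. No outcome is involved.
2. Change on the HAM-A and responder status by week 20 (W20) in the stopped group: "along with the degree to which any patients randomized to discontinue demonstrate additional symptom improvement (using HAM-A ratings) in the absence of treatment".
3. The relation of the Session 5 score to response, again in the stopped group: "We will also explore whether patterns exist between S5 MEAQ-DA scores and responder status for those that discontinued after session 6".

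The only between-arm model in the section compares the three module-ordering conditions. Treatment length is not named in it.

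A comparator for stopping exists by design. The Study Design section says: "All participants will also be randomized to two treatment-duration conditions: 1) Brief: 7 sessions; or 2) Full: 13 sessions". Research Procedures schedules the assessment visits for all participants and 20 weeks of weekly questionnaires for both lengths: "patients in the Brief condition will continue to complete these questionnaires after discontinuing treatment". The Power Analyses section speaks in general terms of effect sizes and their variability, without naming a length effect.

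**The concern.** Using a marker to prompt stopping is a comparative decision. It requires knowing how patients with a given score fare if they stop and how similar patients fare if they continue. Both outcome-linked analyses describe only the first group. They can show who does well after brief treatment. They cannot show whether those patients would have done better with more sessions, or whether the gap between continuing and stopping changes with MEAQ-DA.

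The pilot is meant to inform a later, well-powered trial. A strong association in the Brief arm could be taken as support for a MEAQ-DA-based stopping rule when the score merely predicts outcome under either length. The randomised data that could address the question would be collected but, on the plan as written, not used for it.

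**Working it through.** The plan gives no effect size, power or responder rate for this aim, so there is no figure to reproduce. All rates below are assumptions.

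**Step 1. A purely prognostic marker still produces a pattern in the Brief arm.** Assume a bivariate normal marker and outcome with correlation *r*, a median split on Session 5 MEAQ-DA, 50% response in the Brief arm, and better response with lower scores. The responder rates in the low and high halves are 0.5 ± arcsin(*r*)/π:

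| *r* | Low half | High half |
|---|---|---|
| 0.3 | 59.7% | 40.3% |
| 0.4 | 63.1% | 36.9% |
| 0.5 | 66.7% | 33.3% |

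These gaps appear even if stopping has the same effect at every score.

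**Step 2. One Brief-arm result fits different truths.** Fix the Brief arm at 63% (low) and 37% (high) and vary the Full arm:

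| Assumed truth | Full, low / high | Brief minus Full, low / high (points) | Brief-only gap |
|---|---|---|---|
| Stopping costs nothing | 63 / 37 | 0 / 0 | 26 |
| Stopping costs everyone | 78 / 52 | −15 / −15 | 26 |
| Stopping costs only the high half | 63 / 63 | 0 / −26 | 26 |

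The planned analyses see only the last column. Of these three patterns, only the third has MEAQ-DA separating patients who lose by stopping from those who do not.

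**Step 3. Precision of the missing contrast.** Assume 1:1 length allocation, no dropout, N/4 patients per cell and 50% response. The 95% half-widths are:

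- Brief minus Full within one half: 1.96 × √(2 × 0.25 / (N/4))
- Difference between the two halves: 1.96 × √(4 × 0.25 / (N/4))

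The documents give several sample sizes: 60 completers (Exclusion Criteria), 80 (Project Information and planned enrolment), 150 (Study Design), and 50 enrolled to date (Continuation Review).

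| N | Per cell | Within one half | Between halves |
|---|---|---|---|
| 50 | 12.5 | ±39 points | ±55 points |
| 60 | 15 | ±36 points | ±51 points |
| 80 | 20 | ±31 points | ±44 points |
| 150 | 37.5 | ±23 points | ±32 points |

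For mean HAM-A change within one half, 1.96 × √(2/(N/4)) gives ±0.72, ±0.62 and ±0.45 SD at N = 60, 80 and 150.

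**Step 4. Chance of detecting the third pattern.** The true difference between halves is 0.26. Every cell has variance 0.63 × 0.37, so SE = √(4 × 0.63 × 0.37 / (N/4)). Under a normal approximation the interval excludes zero in 18%, 23% and 38% of trials at N = 60, 80 and 150.

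These figures are best cases. Length is assigned only shortly before Session 5 ("Before the start of Treatment Session 5, clinician participants will alert study staff"), so patients lost earlier never reach that randomisation.

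**The case against.** The strongest defence is that the analysis fits what was asked. The second objective concerns change within briefer treatment, the Background asks what predicts success there, and being an early indicator of response is a prognostic question. The aim is exploratory, and the plan nowhere says the pilot will establish a stopping rule. All of this stands and is why the point is minor. It does not cover the further step of letting the score prompt discontinuation, which the same sentence of the plan names.

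Second, the Brief arm is not wholly uninformative about the cost of stopping, because response under continued treatment cannot exceed 100%. If low-scoring Brief patients responded at 90% (an assumption), continuing could add at most 10 points. That is correct, but it only bounds the cost. At 63% response the bound is 37 points.

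Third, the proposed table is too imprecise to separate the scenarios in Step 2. That is also correct. But the planned low-versus-high comparison inside the Brief arm rests on the same cell sizes, so under the same assumptions its half-width is also ±36, ±31 and ±23 points. Imprecision does not favour the planned analysis.

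Fourth, the Statistical Design text reads like an extract from a longer proposal, and a length contrast could be stated elsewhere. The claim is therefore limited to these documents.

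Finally, the follow-up is not entirely clean. HAM-A is listed for assessment visits but not for the weekly battery. Visit 3 falls at weeks 13–16, while the Full window is 20 weeks and the analysis refers to W20. This conflict already affects the plan's own responder analysis and must be reconciled in any case.

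**Conclusion.** The concern holds, as a minor point. As written, the plan can address whether Session 5 MEAQ-DA predicts outcome after brief treatment. It cannot show that the score should prompt stopping, because neither outcome-linked analysis includes patients who continued and these documents state no Brief-versus-Full outcome contrast. That conclusion is a matter of logic and does not depend on the assumed rates. The sizes do depend on them: a 26-point Brief-arm gap is compatible with a cost of stopping of 0, 15 or 26 points in the high half and of 0 or 15 points in the low half. The precision figures rest on 1:1 allocation, a median split, 50% response and no dropout. A confirmatory test of the contrast is not realistic at any sample size the documents give.

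**What to change.** - In all patients randomised to length, analysed as randomised, add an exploratory table of responder rates and mean HAM-A change by length arm and Session 5 MEAQ-DA half, using one median pooled over both arms. Report Brief-minus-Full differences with 95% confidence intervals and make no claim of a test.
- Use a MEAQ-DA score recorded before the length allocation is revealed, and say so. The weekly pre-session measure can supply it. Assessment Visit 2, between Sessions 5 and 6, comes after allocation is requested.
- Define responder, which these documents do not do, and apply the definition identically in both arms.
- Optionally, to avoid losing information by splitting the score, fit continuous HAM-A with a length-by-MEAQ-DA term, adjusted for baseline HAM-A.
- State that the Brief-only pattern is prognostic. If nothing else is changed, this sentence alone prevents the over-reading.
- Reconcile the passages on the W20 time point so that both arms share one endpoint.

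The cost is one four-cell table and two or three sentences of analysis-plan wording, using measures already scheduled in both arms. The W20 reconciliation is needed for the existing analysis anyway. The drawback is wide intervals, which should be stated alongside the table so that it is used for planning only.
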